10.1 Measures to Minimize Bias

10.1.1 Enrollment/Randomization/Masking Procedures

Subjects will be assigned a de-identified subject number upon enrollment in the study. Subjects will be randomly assigned to one of two study groups in a 1:1 ratio just before receiving anesthesia; 0.5%

CONFIDENTIAL

This material is the property of the NYU School of Medicine and Langone Medical Center. Do not disclose or use except as authorized in writing by the study sponsor

Bupivacaine with 1:200,000 epinephrine OR 2% Lidocaine with 1:100,000 epinephrine. The randomization schema will be provided by the unblinded statistician and will be implemented using the REDCap randomization module.

Two PG students, who are only delegated for the study agent accountability procedures and blinding and randomization procedures will wrap all of the drug cartridges of Bupivacaine with opaque tape and a cartridge number assigned by Biostatistics prior to recruitment and place them in a container which will have the name of the drug. The same procedure will be done for the Lidocaine group. These two containers will be stored in a locked cabinet on 7th floor.

At the time when a subject is recruited by the treating resident and is found eligible and signs a consent, one of the 2 PG students will be notified and will log onto REDCap and retrieve the randomization for the subject within the appropriate stratum (lidocaine/ Bupivacaine) pick up a pair of pre-wrapped cartridges in accordance with the randomization scheme, write on the wrapped cartridges the assigned subject number in the consult room on the 7th floor, privately in order to prevent unintentional unblinding, log in the subject number with the corresponding numbers of the pair of cartridges, and hand it to the treating resident.

10.1.2 Breaking the Study Blind/Participant Code

The blind will be broken for the individual, if IANB doesn't provide adequate soft tissue numbness after 15 minutes after the second cartridge of anesthesia was administered because the method of injection of LA might change if IANB doesn't provide adequate lip numbness after 2nd injection. The blind will also be broken for those subjects who need supplemental injections more than 2 times because of reporting of more than mild pain when being worked on as shown in the algorithmic chart for anesthetic administration in Fig. 1 The subject will be excluded from the study. If number of supplemental injections increases, the injections themselves may also contribute to postoperative pain and discomfort.

In case of AE, SAE or UP, the blind will be broken for the individual. It will be reported to the PI. If unblinding occurs because of an emergency situation such as AE, SAE or UP, the PI will be informed. If it is an emergency AE, SAE or UP, the attending faculty; NYS Licensed Co-Investigators on the floor may be the first one to reach out to before the PI can be present on the floor by the treating PG student. The Co-Investigator will call to access medical emergency if any such event occurs. Resuscitative equipment and personnel for treating adverse reactions will be immediately available. If it is a delayed AE, such as persistent anesthesia that lasted more than the expected period, the subject will inform the PI and PI will be responsible for any additional clinical examination and diagnosis and referrals.

11 Source Documents and Access to Source Data/Documents

Source data is all information, original records of clinical findings, observations, or other activities in a clinical trial necessary for the reconstruction and evaluation of the trial. Source data are contained in source documents. The sources of the documents are the preoperative questionnaires, immediate and follow-up postoperative questionnaire collected either on paper form or in REDCap. Also, questionnaire regarding subject's preoperative clinical examination and diagnosis, intraoperative data will be collected in a questionnaire from the treating PG student. All source documents will be stored securely in REDCap. Paper forms or documents will be securely locked on 4th floor room 407 and will be only be accessible to study team.

Access to study records will be limited to IRB-approved members of the study team. The investigator will permit study-related monitoring, audits, and inspections by the IRB, the government regulatory bodies, and University compliance and quality assurance groups of all study related documents (e.g. source documents, regulatory documents, data collection instruments, study data etc.).

Participation as an investigator in this study implies acceptance of potential inspection by government regulatory authorities and applicable University compliance and quality assurance offices.

CONFIDENTIAL

12 Quality Assurance and Quality Control

Quality control (QC) procedures will be implemented beginning with the data entry system and data QC checks that will be run on the database will be generated. Any missing data or data anomalies will be communicated to the site(s) for clarification/resolution.

Following written standard operating procedure (SOP), the monitors will verify that the clinical trial is conducted and data are generated, documented (recorded), and reported in compliance with the protocol. The investigational site will provide direct access to all trial related sites, source data/documents, and reports for the purpose of monitoring and auditing by the sponsor, and inspection by local and regulatory authorities.

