The solutions also contain sodium metabisulfite, a sulfite that may cause allergic-type reactions including anaphylactic symptoms and life-threatening or less severe asthmatic episodes in certain susceptible people. The overall prevalence is very low. Subjects who have sodium metabisulfite allergies will be excluded from the study.

Any adverse reaction that could be caused by bupivacaine is similar, if not identical, to lidocaine because both have a similar chemical composition, both are amide type LA, and both are commonly and interchangeably used in dental practice (10, 27). With all routine precautions taken, exceeding the recommended plasma level and reaching toxic concentrations thus the occurrences of adverse events are reported to be rare during dental treatments.

When the study agent, bupivacaine HCl 0.5% with epinephrine, is used for dental injections, the long duration of anesthesia (7 hours) could increase the possibility of inadvertent biting trauma to tongue, lips, and buccal mucosa. Subjects will be advised not to chew solid foods or test the anesthetized area by biting or probing until normal sensation has returned. Subjects may have difficulty in eating, drinking, talking for a longer period of time, which might affect them physically and psychosocially. However, postoperative pain may also limit subjects' orofacial functioning and wellbeing, which is eliminated by LLA. Therefore, the information to be gained regarding the overall efficacy of bupivacaine by using OHIP-14 is significant and outweighs the risks involved.

Subjects will be asked to spend time filling out questionnaires before and after treatment. We have limited the amount of questions per document to save the subject time. Subjects can complete these questionnaires alone if preferred, or if the subject feels uncomfortable answering any of the questions, they can tell the study coordinator or the PI. Although there is a minor risk for loss of privacy in this study, confidential data collected for research purposes will be labeled with a unique de-identified study subject number and stored securely.

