8.1.1 Definition of Adverse Events (AE)

An **adverse event** (AE) is any symptom, sign, illness or experience that develops or worsens in severity during the course of the study. The adverse events for the study and control agent can be found on the attachment of the agents' package insert. Abnormal results of diagnostic procedures are considered to be adverse events if the abnormality:

- results in study withdrawal
- is associated with a serious adverse event
- is associated with clinical signs or symptoms
- leads to additional treatment or to further diagnostic tests
- is considered by the investigator to be of clinical significance

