8.2 Classification of an Adverse Event

8.2.1 Severity of Event

For AEs not included in the protocol defined grading system, the following guidelines will be used to describe severity.

- **Mild** – Events require minimal or no treatment and do not interfere with the participant's daily activities.

CONFIDENTIAL

This material is the property of the NYU School of Medicine and Langone Medical Center. Do not disclose or use except as authorized in writing by the study sponsor

- **Moderate** – Events result in a low level of inconvenience or concern with the therapeutic measures. Moderate events may cause some interference with functioning.
- **Severe** – Events interrupt a participant’s usual daily activity and may require systemic drug therapy or other treatment. Severe events are usually potentially life-threatening or incapacitating.

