8.3 Time Period and Frequency for Event Assessment and Follow-Up

The occurrence of an AE or SAE may come to the attention of study personnel during study visit or during the remote follow up period. All AEs including local and systemic reactions not meeting the criteria for SAEs will be captured. Information to be collected includes event description, time of onset, clinician’s assessment of severity, relationship to study product (assessed only by those with the training and authority to make a diagnosis), and time of resolution/stabilization of the event. All AEs occurring while on study must be documented appropriately regardless of relationship. All AEs will be followed to adequate resolution.

Any medical condition that is present at the time that the participant is screened will be considered as baseline and not reported as an AE. However, if the study participant’s condition deteriorates at any time during the study, it will be recorded as an AE. UPs will be recorded in the data collection system throughout the study.

CONFIDENTIAL

This material is the property of the NYU School of Medicine and Langone Medical Center. Do not disclose or use except as authorized in writing by the study sponsor

Changes in the severity of an AE will be documented to allow an assessment of the duration of the event at each level of severity to be performed. AEs characterized as intermittent require documentation of onset and duration of each episode.

The PI will record all reportable events with start dates occurring any time after informed consent is obtained until the last day of study participation. At each study visit, the investigator will inquire about the occurrence of AE/SAEs since the last visit. Events will be followed for outcome information until resolution or stabilization.

All unresolved adverse events should be followed by the investigator until the events are resolved, unless the subject is lost to follow-up, or the adverse event is otherwise explained. At the last scheduled visit, the investigator should instruct each subject to report any subsequent event(s) that the subject, or the subject's personal physician, believes might reasonably be related to participation in this study.

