13.3 Informed Consent Process

13.3.1 Consent and Other Informational Documents Provided to Participants

Consent forms describing in detail the study procedures, and risks are given to the participant and written documentation of informed consent is required prior to starting intervention/administering study product. Each participant will be given a copy of the consent form to bring home. This will include contact information for the PI.

Potential subjects will be informed that the purpose of the study is to compare their oral quality of life and pain resolution with two different standard of care dental anesthetics postoperatively. They will be informed about possible, risks and benefits.

In order to successfully blind the subjects, they will not be informed of the names and differences in duration of two types of study product used in the study. Subjects will be informed that both products are FDA

CONFIDENTIAL

approved, commercially available and routinely used in the NYU Dentistry clinics. They will also be informed that the products are used to provide soft tissue anesthesia between 3-7 hours.

It is important to blind the subjects in terms of the differences of duration of the two products because the outcome measures are patient centered and any bias could affect the study results and prevent objective data collection. When the participant returns for the second treatment visit for the completion of the treatment, they will be debriefed and told which product they received.

The following materials are submitted with this protocol:

- Screening and eligibility form
- Key information form
- Consent form
- Subject contact form
- Debriefing script

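### The rule in 10.1.2 opens the individual code for every adverse event, with no test of severity, relatedness or need, and does not say who may be told before the self-reported day 1 and day 5 OHIP-14

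*Combined protocol and SAP*

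**What the plan says.** Section 10.1.2 first lists two intraoperative reasons for unblinding: failed lip numbness after the second block, and more than two rounds of supplemental injection. It then adds a general rule: "In case of AE, SAE or UP, the blind will be broken for the individual". The rest of that paragraph covers emergencies, but also a delayed event, with anesthesia outlasting its expected period as the example.

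The safety sections make the trigger wide:

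- Section 8.1.1 defines an adverse event as "any symptom, sign, illness or experience that develops or worsens in severity during the course of the study".
- Section 8.2.1 describes the mildest grade as "Events require minimal or no treatment and do not interfere with the participant's daily activities".
- Section 8.3 says "All AEs including local and systemic reactions not meeting the criteria for SAEs will be captured", and also "All AEs occurring while on study must be documented appropriately regardless of relationship". Recording runs from consent to the last day of participation.

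The primary endpoint (4.1.1) is the change in OHIP-14 to day 1 and to day 5. Sections 13.3.1 and 13.3.2 withhold the drug names and durations from patients because the outcomes are patient centered and "any bias could affect the study results and prevent objective data collection". Patients are to learn their assignment at the second treatment visit.

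On event frequency by arm, section 2.4.1 says of bupivacaine that "the long duration of anesthesia (7 hours) could increase the possibility of inadvertent biting trauma to tongue, lips, and buccal mucosa". The same section describes adverse reactions to the two drugs as similar or even identical.

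**The concern.** A code break is normally reserved for cases where knowing the treatment changes what is done for the patient. Here the trigger is the event itself, and by the definitions above that event may be mild and unrelated to the anesthetic.

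Three things are at stake.

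- **Patient-reported outcomes.** OHIP-14, pain, analgesic use and numbness are all self-reported between 6 and 120 hours. If an assignment reached the patient in that window, the protection described in 13.3.1 would be lost for that patient.
- **Staff judgements.** Causality is graded by the examining clinician (8.2.2), and the halting rule (8.5) counts events judged probably related. If the code is opened for every event, those judgements may be made unblinded. The PI receives reports of events and examines delayed ones (10.1.2), and also takes calls when rescue medication does not help (7.6). Team members telephone patients who lack internet access to collect outcomes (7.1.1).
- **Analysis.** Section 10.2.1 analyses all randomized patients. No section provides for flagging patients unblinded after an adverse event, or for examining how much they matter.

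**Working it through.** **1. Is the trigger narrowed anywhere?**

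| Possible limit | Where to look | Result |
|---|---|---|
| Severity | 10.1.2, 8.2.1 | None; mild events count |
| Relatedness | 10.1.2, 8.3 | None; events are recorded whatever the cause |
| Clinical need for the code | 10.1.2 | None |
| Emergencies only | 10.1.2 | Suggested by one later sentence, but the same paragraph also covers delayed events |
| Who receives the code after an adverse event | 10.1.2, 13.3 | Not stated |

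The rule stands as unconditional.

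**2. The plan's own design figure.** Inputs from 10.1 (Sample Size Determination): SD 13.3, 40 per arm, two-sided 2.5% per test, difference 9.3, dropout 20%.

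- Standard error of the difference = 13.3 × √(2/40) = 2.97.
- Exact t-test power at 9.3 is 79.8%; the difference detectable with 80% power is 9.32.
- Enrolment = 80 / (1 − 0.20) = 100.

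The stated figures reproduce and are not in dispute.

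**3. Size of a possible bias.** The documents give neither event rates nor the effect of knowing the assignment, so the rates and shifts below are assumptions. Let pB and pL be the shares unblinded before the endpoint in the bupivacaine and lidocaine arms, and b the shift in OHIP-14 change among unblinded patients, in the same direction in both arms. With no true treatment effect:

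spurious difference = b × (pB − pL)

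False-positive rate per test ≈ Φ(−2.241 + shift/2.97) + Φ(−2.241 − shift/2.97)

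| pB vs pL | b (points) | Spurious difference | False-positive rate per test (planned 2.5%) |
|---|---|---|---|
| equal | any | 0 | 2.5% |
| 10% vs 5% | 6 | 6 × 0.05 = 0.3 | 2.6% |
| 20% vs 5% | 6 | 6 × 0.15 = 0.9 | 3.2% |
| 30% vs 10% | 3 | 3 × 0.20 = 0.6 | 2.8% |
| 30% vs 10% | 5 | 5 × 0.20 = 1.0 | 3.3% |
| 30% vs 10% | 6 | 6 × 0.20 = 1.2 | 3.7% |
| 30% vs 10% | 9.3 | 9.3 × 0.20 = 1.86 | 5.5% |

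With 40 per arm, 30% vs 10% means 12 against 4 patients. A difference of 0.6 to 1.0 points is 6% to 11% of 9.3 (0.6/9.3 and 1.0/9.3).

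For both tests together, simulation (20,000 runs, day 1 to day 5 correlation assumed 0.5) gives a familywise error of 4.7% without bias, 5.7% at 20% vs 5% with b = 6, and 6.6% to 8.8% at 30% vs 10% with b = 6 to 9.3. Error becomes large only under extreme assumptions: 12.4% to 23.4% at 50% vs 10% with the same shifts.

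**The case against.** The case for leaving the sentence alone has real substance.

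- **No section says the patient is told.** Breaking the blind for an individual identifies whose code is opened, not who sees it. Where a recipient is named for intraoperative failures, it is the treating dentist (5.8.2, 6.1.7, 7.1.1). The only disclosure to patients that is described is the later debriefing. A reader might infer that the rule hands patients their assignment; the documents leave that open. Nor do they say that the PI always learns the code, only that the PI is informed.
- **Many mild events may surface late.** The investigator asks about events at study visits (8.3), and the next scheduled visit is typically weeks later (5.6, 7.2.4), after day 5. The remote surveys cover pain, analgesics, numbness and OHIP-14, with no separate adverse-event question described. This stands as a limit on frequency. It does not close the window, because 8.3 also expects events to come to light during remote follow-up, and unscheduled visits are possible (7.2.6).
- **Arm imbalance is not established.** A reader might infer from 2.4.1 that the protocol expects more events with bupivacaine. It says only that biting trauma could become more likely, and adds preventive advice. Sections 2.1, 2.2.1 and 2.4.1 also report no safety difference or similar reactions. The delayed-event example in 10.1.2 is tied to neither arm.
- **Emergency unblinding may be what was meant.** One later sentence in 10.1.2 points that way. But the general rule is unconditional and the paragraph extends to non-emergency events, so at best the intention is not what is written.

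Numbness duration may already hint at the arm. That makes the rule an addition to an existing risk, not its only source.

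**Conclusion.** The defect is in the rule and does not depend on any event rate. As written, 10.1.2 requires code breaks that serve no stated purpose, does not name who may learn the result, and can act before the endpoint that 13.3.1 and 13.3.2 set out to protect.

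The consequence is conditional. It is negligible if adverse events are rare or balanced. A same-direction shift of 3 to 5 points gives no bias at equal rates and 0.6 to 1.0 points at 30% against 10% unblinded, both shift and rates being assumed. It becomes material only if events are frequent, unequal, detected before day 5, and the assignment reaches someone who can influence the answers.

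A reader might go further and suppose that knowledge moves scores in opposite directions in the two arms. The rates would then add: (0.10 + 0.10) × 3 to 5 = 0.6 to 1.0 points even at equal rates, and (0.30 + 0.10) × 3 to 5 = 1.2 to 2.0 points at 30% against 10%. Nothing in the documents supports opposite reactions, so those figures should not be used as the expected size.

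The wording is worth correcting because the change is cheap, not because a large bias has been shown.

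**What to change.** Replace the general sentence in 10.1.2 with a need-based rule:

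- The individual code is opened only when the responsible clinician judges that knowing the anesthetic is needed to manage the event, or when reporting rules require it. The decision stays with that clinician.
- The date, time and reason are logged, at the time or afterwards, so that an emergency is not delayed.
- The code goes only to that clinician. The patient and those collecting outcomes stay blinded through the day 5 OHIP-14 where possible.
- All other adverse events, including causality, are assessed blinded.

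In section 10.2, add a summary of code breaks by arm and by timing relative to the day 1 and day 5 questionnaires. Keep the all-randomised analysis as primary. An analysis without code-broken patients may be added as supportive only: it conditions on an event after randomization that may differ by arm, so it can introduce selection bias and cannot cleanly isolate reporting bias.

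The cost is a protocol wording change, one short table and, for each code break, a brief judgement and a log entry. The two postgraduate students who handle randomization and cartridge logs already hold the assignments, so no new role is needed.

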12.1 Data Monitoring Regarding Drug Accountability

One carton containing 5 blisters of 10X1.8 mL of Bupivacaine, in total containing 50 cartridges and one cartoon containing 5 blisters of 10X1.7 mL Lidocaine in total containing 50 cartridges will be obtained initially from the Endodontic supply desk. Those cartons will be stored in a locked cabinet on the 7th floor, which will be only accessible by 2 post graduate (PG) students who are not otherwise part of the trial. The two PG students who are only delegated for the study agent accountability procedures.

A study product log will be created and maintained by the 2 PG students assigned ([name] and [name]). The study product log will be signed and dated each time one of the two PG student removes a pair of cartridges. New cartons will be obtained from the supply desk when necessary and documented in the log. The two PG students will be responsible for maintaining this log and will reconcile the log each week assigned, to document drug consumed, and remaining.

13 Ethics/Protection of Human Subjects

